#### **12.4. Deaths and Serious Adverse Events**

In the event that a subject has withdrawn consent, no data after the withdrawal of consent date from this subject including death is supposed to appear in the database, which should be part of the data cleaning process. All deaths will be summarised based on the number and percentage of subjects. This summary will classify subjects by time of death relative to the last dose of medication (>60 days or ≤60 days) and primary cause of death (disease under study, SAE related to study treatment, or other). A supportive listing will be generated to provide subject-specific details on subjects who died.

All SAEs will be tabulated based on the number and percentage of subjects who experienced the event. SAEs will be summarized up to 60 days after last infusion. Separate summaries will also be provided for study treatment-related SAEs, fatal SAEs and study treatment related fatal SAEs. The summary tables will be displayed in descending order of total incidence OR incidence by PT only.

A study treatment-related SAE is defined as an SAE for which the investigator classifies the relationship to study treatment as “Yes”. A worst case scenario approach will be taken to handle missing data, i.e. the summary table will include events with the relationship to study treatment as ‘Yes’ or missing.

SAEs are included in the listing of all adverse events. Separate supportive listings with subject-level details will be generated for

- Fatal SAEs
- Non-Fatal SAEs.

#### **12.5. Adverse Events Leading to Discontinuation of Study Treatment and/or Withdrawal from the Study and Other Significant Adverse Events**

The following categories of AEs will be summarized separately in descending order of incidence by PT only and separate supportive listings will be generated with subject level details for those subjects:

- AEs Leading to Discontinuation of Study Treatment
- AEs leading to Withdrawal from the Study
- AEs Leading to Dose Interruptions/Delays

- AEs Leadings to Dose Reductions

## 12.6. Pregnancies

While pregnancy itself is not considered to be an AE or SAE, any pregnancy complication or elective termination of a pregnancy for medical reasons will be recorded as an AE or SAE as described in the protocol. If subjects become pregnant while on the study, the information will be included in the narratives and no separate table or listing will be produced.

## 12.7. Clinical Laboratory Evaluations

Hematology and clinical chemistry data will be summarized for each parameter by scheduled assessment. The proportion of subjects with values outside the reference range for each of these laboratory parameters will be summarized by scheduled assessment and overall at any post-baseline assessment.

The CTCAE v4.0 / IWCLL Grading Scale for Hematological Toxicity will be used to programmatically assign grades to the laboratory values. The laboratory values will be summarized by frequency and percentage of subjects at each time interval by maximum grade. The worst grade per subject per time interval will be reported along with the worst grade per subject.

Summary statistics of laboratory values and changes from baseline at each assessed time interval will include count, mean, median, standard deviation, minimum, and maximum. Baseline is defined as the assessment closest to but prior to first dose (e.g. day 1 if available otherwise screening).

Summaries of subject shifts in grade will be provided. These summaries will display the number and percentage of subjects with a maximum grade during each assessment time based on their baseline grade.

Summaries of worst case grade increase from baseline grade will be provided for all the lab tests that are gradable by CTCAE v4.0. These summaries will display the number and percentage of subjects with a maximum post-baseline grade increasing from their baseline grade. Any increase in grade from baseline will be summarized along with any increase to a maximum grade of 3 and any increase to a maximum grade of 4. Missing baseline grade will be assumed as grade 0. For laboratory tests that are graded for both low and high values, summaries will be done separately and labeled by direction, e.g., sodium will be summarized as hyponatremia and hypernatremia

Separate summary tables for hematology and chemistry laboratory tests will be produced.

Detailed derivation of baseline assessment is specified in Section [9.2.7](#).

Unless otherwise specified, the denominator in percentage calculation at each scheduled visit will be based on the number of subjects with non-missing value at each particular visit.

The hepatobiliary laboratory values will also be summarized.

Listings for lab data for subjects with abnormalities of potential clinical concern will be provided. Figures for median hemoglobin/neutrophil count/platelet count for all subjects, and for all subjects excluding those who received blood supportive care products over time will also be generated.

### **12.7.1. Analyses of Liver Function Tests**

Summaries of hepatobiliary laboratory events including possible Hy's law cases will be provided.

Possible Hy's law cases are defined as any elevated  $ALT > 3 \times ULN$  and total bilirubin  $\geq 2 \times ULN$  ( $\geq 35\%$  direct bilirubin; bilirubin fractionation required);  $ALT > 8 XULN$ ;  $ALT \geq 5XULN$  for more than 2 weeks.

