6.4.1.1. Liver Chemistry Stopping Criteria

1. ALT > 3xULN **and** bilirubin \geq 2xULN (>35% direct bilirubin; bilirubin fractionation required*)
2. ALT > 8xULN
3. ALT \geq 5xULN for more than 2 weeks

**NOTE: serum bilirubin fractionation should be performed if testing is available. If testing is unavailable and a subject meets the criterion of total bilirubin >2.0 xULN, then the following actions must still be performed.*

When any of the liver chemistry stopping criteria is met, do the following:

- **Immediately** withdraw investigational product
- Report the event to Novartis **within 24 hours** of learning its occurrence
- Complete the liver event CRF and SAE data collection tool if the event also meets the criteria for an SAE. All events of ALT $\geq 3 \times$ ULN **and** bilirubin $\geq 2 \times$ ULN ($>35\%$ direct bilirubin), termed 'Hy's Law', **must be reported as an SAE**.

NOTE: serum bilirubin fractionation should be performed if testing is available. If testing is unavailable, **record presence of detectable urinary bilirubin on dipstick**, indicating direct bilirubin elevations and suggesting liver injury.

- Complete the liver imaging and/or liver biopsy CRFs if these tests are performed
- Perform liver event follow up assessments, and monitor the subject until liver chemistries resolve, stabilize, or return to baseline values as described below.
- Withdraw the subject from the **study** (unless further safety follow up is required) after completion of the liver chemistry monitoring as described below.
- Do not re-challenge with investigational product.

In addition, for criterion 1:

- Make every reasonable attempt to have subjects return to clinic **within 24 hours** for repeat liver chemistries, liver event follow up assessments (see below), and close monitoring
- A specialist or hepatology consultation is recommended
- Monitor subjects twice weekly until liver chemistries (ALT, AST, alkaline phosphatase, bilirubin) resolve, stabilize or return to within baseline values

For criteria 2 and 3:

- Make every reasonable attempt to have subjects return to clinic **within 24-72 hrs** for repeat liver chemistries and liver event follow up assessments (see below)
- Monitor subjects weekly until liver chemistries (ALT, AST, alkaline phosphatase, bilirubin) resolve, stabilize or return to within baseline values; criterion 3 subjects should be monitored as frequently as possible.

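### SAP 12.7.1 puts all three protocol liver stopping criteria under 'possible Hy's law', so isolated ALT elevations would be counted under a term the protocol keeps for combined ALT and bilirubin elevation

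*SAP*

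**What the plan says.** SAP 12.7.1 announces "Summaries of hepatobiliary laboratory events including possible" Hy's law cases. The definition follows at once: "law cases are defined as any elevated", then three limbs separated by semicolons.

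- Limb 1: ALT >3xULN with total bilirubin ≥2xULN, at least 35% of it direct. The bracketed qualifier reads "direct bilirubin; bilirubin fractionation required".
- Limb 2: ALT >8xULN.
- Limb 3: ALT ≥5xULN "for more than 2 weeks".

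Protocol 6.4.1.1 gives the same three limbs, in the same order, as numbered stopping criteria; the third is ALT at or above "5xULN for more than 2 weeks". Their purpose is to trigger a set of actions: "When any of the liver chemistry stopping criteria is met, do the following". The Hy's law name appears later in that section and is attached to one group only: ALT ≥3xULN with bilirubin ≥2xULN (above 35% "direct bilirubin), termed 'Hy's Law"). Events in that group "must be reported as an SAE". Any other event that meets a stopping criterion goes on the SAE form only if it is serious in its own right.

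**The concern.** The SAP appears to have taken a stopping-rule list and given it the name of one of its members. Hy's law, as the protocol uses the term, requires ALT and bilirubin to be raised together. Limbs 2 and 3 drop the bilirubin requirement, so a programmer who follows 12.7.1 would flag subjects whose bilirubin never moved.

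What is at stake is the meaning of a labelled count in a safety summary. A reader who knows the protocol's definition would take the count to be combined elevations. Someone comparing it with the events reported as SAEs under the protocol's Hy's law rule would find subjects in the one who need not be in the other.

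The definition is not repaired later. The plan for the 280-event analysis (Section 1) says its data rules follow those of the interim report. The plan for the final analysis (Section 1) says its conventions follow the previous SAP. Neither redefines the term.

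**Working it through.** The plan gives no figure to reproduce, so the check sets the definitions side by side and applies them to test values.

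| Element | Protocol 6.4.1.1, stopping criteria | Protocol 6.4.1.1, Hy's law sentence | SAP 12.7.1, possible Hy's law |
|---|---|---|---|
| ALT with bilirubin | ALT >3xULN and bilirubin ≥2xULN, >35% direct | ALT ≥3xULN and bilirubin ≥2xULN, >35% direct | ALT >3xULN and total bilirubin ≥2xULN, ≥35% direct |
| High ALT alone | ALT >8xULN | not included | ALT >8xULN |
| Prolonged ALT alone | ALT ≥5xULN, >2 weeks | not included | ALT ≥5xULN, >2 weeks |
| Fractionation unavailable | actions still required if total bilirubin >2.0xULN | dipstick urinary bilirubin recorded instead | fractionation required, no provision |

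**Could the bilirubin condition carry over to limbs 2 and 3?** If it did, both limbs would be redundant. ALT >8xULN and ALT ≥5xULN each imply ALT >3xULN, so every such subject would already satisfy limb 1. The two limbs have an effect only if they stand on ALT alone, which is also how the punctuation reads.

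**Test values**

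| Case | ALT | Bilirubin | SAP 12.7.1 | Protocol Hy's law sentence |
|---|---|---|---|---|
| a | 9xULN | 1xULN | counted (limb 2) | not counted |
| b | 6xULN for 3 weeks | 1xULN | counted (limb 3) | not counted |
| c | 4xULN | 2.5xULN, 50% direct | counted | counted |
| d | exactly 3xULN | 2.5xULN, 50% direct | not counted | counted |
| e | 4xULN | 2.5xULN, exactly 35% direct | counted | not counted |
| f | 4xULN | 2.5xULN, not fractionated | not countable as written | direct fraction unknown; fallback provided |

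Cases a and b establish the point. Cases d and e are boundary differences. Case d reflects a conflict inside Protocol 6.4.1.1, where criterion 1 has ALT >3xULN and the Hy's law sentence has ≥3xULN. Case f can arise because scheduled biochemistry (Protocol 6.3.2) lists total bilirubin only. Fractionation is a follow-up test (Protocol 6.4.1.2), to be done where it is available.

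**Does the protocol keep the groups apart elsewhere?** Yes. Criterion 1 has its own return time and monitoring frequency in 6.4.1.1. Section 6.4.1.2 makes autoantibody tests and liver imaging mandatory for the combined elevation and optional for other liver abnormalities.

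**The case against.** The mismatch itself is hard to dispute. The stronger objections concern its consequence.

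- **No listed output is titled Hy's law.** The liver tables in both later plans are 3.1230 (liver signal or event), 3.1240 (time to liver event) and 3.1250 (subjects meeting liver stopping criteria). The three-limb list fits 3.1250, which is correctly named. This stands. A row inside one of these tables could still carry the label, but Section 12 of the SAP puts the list of displays in a separate document. A reader might infer that a liver table will certainly report false Hy's law cases; the documents show only that the definition, if followed, would produce them.
- **The count is not a leading result.** Hy's law is neither an endpoint (SAP 2) nor an adverse event of special interest (SAP 12.3). A reader might treat it as a headline safety figure; nothing in the documents gives it that standing.
- **The size is unknown.** One could assume that 1% to 2% of about 240 ofatumumab subjects have isolated elevations, which gives 2.4 to 4.8 extra cases. The documents offer no rate to support this, and zero is equally compatible with them.
- **Failure to reconcile with SAEs has other causes.** A laboratory-derived count and investigator reports come from different sources. The cut-off differences and missing fractionation would separate them even after limbs 2 and 3 were removed. This also stands.
- **Limbs 2 and 3 over-include, so they hide nothing.** This is true of those limbs. Limb 1 can miss cases (d and f above).
- **The word 'possible' allows latitude.** It can mean that other causes have not been excluded, but it does not remove the bilirubin component.

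**Conclusion.** The point holds as an error of definition. As written, SAP 12.7.1 would count a subject with ALT >8xULN, or with ALT ≥5xULN for more than 2 weeks, as a possible Hy's law case even when bilirubin is normal. Protocol 6.4.1.1 does not use the term that way. The effect is confined to a descriptive hepatobiliary summary. PFS and the inferential secondary endpoints are untouched.

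The number of subjects affected cannot be derived from the documents. The conclusion rests on reading the semicolons as alternatives, which is the only reading that gives limbs 2 and 3 any effect, and on the unseen table shells following 12.7.1. Confidence is high in the textual mismatch and low in any statement about how many cases it would add.

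**What to change.** In SAP 12.7.1, restrict possible Hy's law to the combined ALT-and-bilirubin criterion. Report ALT >8xULN, and ALT ≥5xULN for more than 2 weeks, only as liver stopping criteria. Table 3.1250 already has that title, and listings 23.0350, 23.0360 and 23.0370 support it at subject level, so no information is lost.

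In the same edit:

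- Reconcile the ALT cut-off (>3 or ≥3xULN), which differs within Protocol 6.4.1.1 as well as between the protocol's Hy's law sentence and the SAP.
- Reconcile the direct-bilirubin cut-off (≥35% in the SAP, >35% in the protocol).
- State how subjects without a fractionation result are handled, in line with the protocol's provision for them, so that they are not dropped. Note that the protocol's fallback uses total bilirubin >2.0xULN where the criterion itself has ≥2xULN.

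Which cut-off applies is for the sponsor to settle; the need is for one version across the sections. The cost is a short edit to one SAP definition and, if any shell carries the label, one table shell. No stopping rule, data collection or analysis model changes.

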### **12.8. Other Safety Measures**

Unless otherwise specified, the denominator in percentage calculation at each scheduled visit will be based on the number of subjects with non-missing value at each particular visit.

#### **Vital Signs**

Vital sign data, as well as change from baseline, will be summarized for each parameter by scheduled assessment. Summary statistics of values and changes from baseline at each assessed time interval will include count, mean, median, standard deviation, minimum, and maximum. Baseline is defined as the assessment closest to but prior to first dose without time (e.g., Day 1 if available otherwise screening).

Summaries of increases in each vital sign at each planned assessment time and the worst-case post baseline value will be produced. Increases will be categorized as follows:

- Systolic Blood Pressure: 'Any Grade Increase', 'Increase to Grade 2 (140-159)' and 'Increase to Grade 3 ( $\geq 160$ )'
- Diastolic Blood Pressure: 'Any Grade Increase', 'Increase to Grade 2 (90-99)', 'Increase to Grade 3 ( $\geq 100$ )'
- Heart Rate: 'Decrease to  $< 60$ ', 'Increase to  $> 100$ '
- Temperature: 'Decrease to  $\leq 35$ ', 'Increase to  $\geq 38$ '

Summaries of shift from baseline values for each planned assessment time and the worst-case post baseline will be provided for all vital signs. Shifts will be categorized at baseline and each planned assessment times as follows:

- Systolic Blood Pressure: ' $< 120$ ', '120-139', '140-159', ' $\geq 160$ '
- Diastolic Blood Pressure: ' $< 80$ ', '80-89', '90-99', ' $\geq 100$ '
- Heart Rate: ' $< 60$ ', '60-100', ' $> 100$ '
- Temperature: ' $\leq 35$ ', '36-37', ' $\geq 38$ '

Vital signs (blood pressure, heart rate, temperature, respiration rate, and weight) will be listed for each subject.

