6.1.7. Vital Signs

Vital signs including temperature, blood pressure (BP), and pulse are documented per Appendix 1 Time and Events and during ofatumumab intravenous infusions. Temperatures for individual subjects must be measured using the same method at all visits.

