### 9.2.7. Baseline Definition

Baseline will be defined as the most recent, non-missing value prior to or on the first study treatment dose date for subjects randomized to the ofatumumab arm. For subjects randomized to the observation arm, baseline will be defined as the most recent, non-missing value prior to or on the randomization date.

For laboratory data, baseline will be defined as the most recent, non-missing value from a central laboratory prior to or on the first study treatment dose date. For subjects randomized to the observation arm, baseline will be relative to the randomization date. If there are no central labs collected for a subject and lab test prior to or on the first dose of study treatment, the most recent, non-missing value from a local laboratory prior to or on the first dose of study treatment (or randomization date for the observation arm) will be defined as the baseline value.

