- For findings, including ECOG status, laboratory data, imaging data, vital signs, constitutional symptoms, lymph node examination, organ examination, and biomarker if the date/time is equal to start date/time of study treatment, the flag will be set to pre-treatment. If time is not available and the date is equal to start date of study treatment, the flag will be set to pre-treatment. If the date is missing, the flag will be set to on-treatment.

**Post-treatment** is defined as any time beyond the on-treatment period.

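### The temperature classes in the vital-sign shift table leave 35.1–35.9 and 37.1–37.9 °C unclassified; secondarily, the baseline text does not secure its own pre-dose intent

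*SAP*

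**What the plan says.** **Classes.** The Vital Signs part of SAP 12.8 plans shift tables for each planned assessment and for the worst post-baseline value. It states: "Shifts will be categorized at baseline and each planned assessment times as follows". The temperature entry is "Temperature: ' $\leq 35$ ', '36-37', ' $\geq 38". SAP 9.4.2 gives the unit as degrees C. No rounding rule or recording precision appears in either document.

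**Denominator.** The opening of SAP 12.8 bases percentages at each scheduled visit on subjects with a non-missing value at that visit, unless otherwise specified.

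**Output.** The temperature shift display is Table 3.1200. It is listed both in the SAP for the 280-event analysis (Appendix 1) and in the final-analysis SAP (Table 1), which carries the earlier analysis conventions forward.

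**Baseline.** For vital signs, SAP 12.8 says "Baseline is defined as the assessment closest to but prior to first dose without time (e.g., Day 1 if available otherwise screening". The general rule in SAP 9.2.7, for the ofatumumab arm, says "Baseline will be defined as the most recent, non-missing value prior to or on the first study treatment dose date"; in the observation arm the reference is the randomization date. Protocol 6.1.7 has vital signs documented at the scheduled visits "and during ofatumumab intravenous infusions". For findings, which include vital signs, SAP 9.3 adds: "If time is not available and the date is equal to start date of study treatment, the flag will be set to pre-treatment".

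**The concern.** A shift table needs every non-missing value to fall in exactly one class. Here two intervals just inside the outer limits belong to none. A subject with a baseline of 37.2 °C and a later reading of 38.5 °C has a classified follow-up value but no baseline row, so the move to 38 or above has no cell. The class percentages also fall short of 100 with no explanation, and a programmer must invent a rule that the SAP does not state.

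Table 3.1200 is, moreover, the only table in the two later output lists that categorises temperature. SAP 12.8 also plans summaries of temperature decreases to ≤35 and increases to ≥38, but the corresponding listed tables cover blood pressure and heart rate for the 280-event analysis and heart rate alone for the final analysis.

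The secondary issue is that two baseline rules for the same data do not agree on the dose date. Only the ofatumumab arm has infusion readings on that date, so any consequence would be one-sided.

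**Working it through.** The plan states no figure on this point, so there is none to reproduce.

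**1. Applying the classes as written.** Take the 31 values from 35.0 to 38.0 °C in steps of 0.1.

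- Class ≤35: 35.0 (1 value)
- Class 36–37: 36.0 to 37.0 (11 values)
- Class ≥38: 38.0 (1 value)
- No class: 35.1–35.9 (9 values) and 37.1–37.9 (9 values), 18 in all

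1 + 11 + 1 + 18 = 31. This counts possible values; it is not a share of readings. At whole-degree resolution no value is lost. The blood-pressure and heart-rate classes in the same section leave no gap on whole numbers, so the defect is confined to temperature.

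**2. Share of readings in the gaps.** The documents give no temperature distribution, so this is an illustration under assumption. For a normal distribution with mean μ and SD σ, recorded to 0.1 °C:

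P(gap) = [Φ((35.95−μ)/σ) − Φ((35.05−μ)/σ)] + [Φ((37.95−μ)/σ) − Φ((37.05−μ)/σ)]

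With μ = 36.6 and σ = 0.4, the lower gap holds 0.052 and the upper gap 0.130, together 0.182. Over the range:

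| Mean (°C) | SD 0.3 | SD 0.4 | SD 0.5 |
|---|---|---|---|
| 36.4 | 8.2% | 18.2% | 27.6% |
| 36.6 | 8.2% | 18.2% | 27.6% |
| 36.8 | 20.5% | 28.1% | 34.2% |

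**3. Effect on the table.** Because the denominator counts non-missing values, the three classes at a visit would add up to between 100 − 34.2 = 65.8% and 100 − 8.2 = 91.8% under these assumptions.

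**4. After the change.** With ≤35.0, >35.0 to <38.0 and ≥38.0, none of the 31 values is unclassified. The outer limits are those that SAP 12.8 and 9.4.2 already use for temperature.

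**5. Baseline texts side by side.** No arithmetic applies.

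- SAP 12.8 requires the reading before first dose, judged without time.
- SAP 9.2.7 takes the latest reading up to and including the dose date.
- Protocol Appendix 1 schedules vital signs at Visit 1, and protocol 6.1.7 adds readings during the infusion, so the dose date can hold readings from before and after the infusion starts.
- SAP 9.3 labels an untimed same-day finding as pre-treatment. That is a study-period flag, not a rule for choosing baseline, and it does not cover a reading timed after the start of the infusion.

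The intent in 12.8 is a pre-dose reading. Without time, that intent cannot be enforced among several readings on one date, and the general rule does not ask for it.

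**The case against.** **On the classes.** Temperature may have been recorded or rounded to whole degrees, in which case nothing is lost. Neither document says so. Rounding would also put 37.5–37.9 in the ≥38 class and 35.1–35.4 in the ≤35 class, against the limits in SAP 9.4.2. It is also fair to say that readings of 37.1–37.9 lie below the SAP's own limit of potential clinical importance. That stands: no reading at or beyond a limit loses its class. What is lost is the mid-range row and any shift that starts or ends in it.

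**On the size.** The percentages rest entirely on assumed distributions. That stands. A reader might infer one definite figure, or a definite share of baseline and follow-up pairs that cannot be placed. The documents support neither, and the pair share would also need the within-subject correlation.

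**On baseline.** A reader might infer that the plan takes infusion readings as baseline for every ofatumumab subject with more than one Day 1 value, and so hides first-infusion reactions. The documents do not support this:

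- SAP 12.8 expressly asks for a reading before first dose.
- SAP 9.2.11 assumes planned Day 1 assessments are done before dosing, although for cycle assignment.
- SAP 9.2.9 reports by nominal visit and keeps unscheduled data to worst-case displays and listings, although it does not clearly bar them from baseline.
- Nothing shows that infusion readings enter the vital-signs dataset in a form that competes for baseline.
- SAP 12.3 analyses infusion reactions from the adverse-event dataset, using events during and within 24 hours after the infusion. That does not depend on the vital-sign baseline, and all vital signs are listed by subject.

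What remains is a wording conflict between two sections.

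**Conclusion.** The temperature gap is a real but minor drafting defect. Followed literally, with readings to 0.1 °C, Table 3.1200 omits readings of 35.1–35.9 and 37.1–37.9 while counting them in its denominator. The share is about 8% to 34% of readings if temperature is roughly normal with mean 36.4–36.8 and SD 0.3–0.5, and zero if it is recorded in whole degrees; none of these inputs comes from the documents.

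The baseline point is secondary. SAP 12.8 and 9.2.7 disagree on whether a dose-date reading must precede the dose, and neither says that readings during or after the infusion are ineligible. Its frequency is unknown, and it does not weaken the capture of infusion reactions.

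Both points touch descriptive safety displays only. PFS, the significance levels, the sample size and the inferential secondary endpoints are unaffected.

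**What to change.** 1. In SAP 12.8, replace the temperature shift classes with ≤35.0, >35.0 to <38.0 and ≥38.0 °C, and apply them in Table 3.1200.
2. In SAP 12.8, with a cross-reference from 9.2.7, state that the vital-sign baseline in the ofatumumab arm is the planned pre-infusion Visit 1 reading, otherwise the screening value, and that readings taken during or after the infusion are not eligible. This does not require discarding a planned Visit 1 reading merely because it has no recorded time.

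The cost is a few lines of SAP text and a small reprogramming of the shift tables. If the planned pre-infusion reading cannot be identified for some ofatumumab subjects, their baseline falls back to screening; the number should be footnoted.
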